7.3 How to take ixazomib

The ixazomib should be taken on an empty stomach, at least 1 hour before or no sooner than 2 hours after a meal. Each capsule should be swallowed separately with a sip of water. A total of approximately 240 mL (about 1 cup/8 oz) of water should be taken with the capsules.

Missed doses can be taken as soon as the patient remembers as long as the next scheduled dose is 72 hours or more away. Patients who vomit a dose after ingestion will not receive an additional dose, but should resume dosing at the time of the next scheduled dose.

Drug will be administered only to eligible patients under the supervision of the investigator or identified sub-investigator(s). The drug will be prepared under the supervision of a pharmacist, or appropriately qualified and trained personnel.

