8.0 Dosage Modification Based on Adverse Events

Strictly follow the modifications in this table for the first **two** cycles, until individual treatment tolerance can be ascertained. Individual drugs can be dose reduced as per the table below depending on the adverse event attribution. Thereafter, these modifications should be regarded as guidelines to produce mild-to-moderate, but not debilitating, side effects. If multiple adverse events are seen, administer dose based on greatest reduction required for any single adverse event observed. Reductions apply to treatment given in the preceding cycle and are based on adverse events observed since the prior dose.

NOTE: If either of pomalidomide or ixazomib is discontinued, the patient can continue on the other drugs, unless specified otherwise in the dose modification tables. If both are discontinued, the patient will go to event monitoring (Section 18.0).

ALERT: ADR reporting may be required for some adverse events (See Section 10)

8.1 Dose Levels for each drug in the combination (Based on Adverse Events in Tables 8.2-4)

NOTE: One drug can be reduced each time based on the drug most likely related to the toxicity observed.

Ixazomib (Days 1, 8, 15)		Pomalidomide (Day 1-21)		Dexamethasone (Days 1, 8, 15, 22)	
Starting dose	4 mg	Starting dose	4 mg	Starting dose	40 mg
-1	3 mg	-1	3 mg	-1	20 mg
-2	2.3 mg	-2	2 mg	-2	12 mg
-3	2.3 mg days 1, 15	-3	1 mg	-3	4 mg
-4	Discontinue	-4	Discontinue	-4	Discontinue

If patients cannot tolerate dose level – 3 of ixazomib AND pomalidomide they will go to event monitoring per Section 18.0. If dexamethasone is discontinued, the patient may continue treatment.

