15.15 Pharmacokinetic information

a) Absorption: After oral dosing, ixazomib is rapidly absorbed with a median T_{max} of 1 hour. The lack of a discernible relationship between BSA and ixazomib clearance over a relatively wide BSA range (1.4-2.6 m²) indicates that total systemic exposure (AUC) following fixed dosing should be independent of the individual patient's BSA. A high-fat meal decreased both the rate and extent of absorption. Therefore, ixazomib should be administered on an empty stomach.

b) Distribution: The steady state volume of distribution is large and is estimated to be 543 L. Ixazomib is 88-94% protein bound.

c) Metabolism: Metabolism is the primary route for elimination of ixazomib by both CYP and non-CYP enzymes. CYP3A4 and 1A2 comprise the major CYP isozymes that contribute to ixazomib metabolism.

d) Excretion: The mean terminal half-life is 9.5 days. Renal elimination is a minor clearance pathway for ixazomib. Dosing adjustment is not required in patients with mild and moderate renal impairment in studies.

However, in a dedicated renal impairment study (C16015), unbound AUC0-last was 38% higher in patients with severe renal impairment or end-stage renal disease (ESRD) requiring dialysis as compared to patients with normal renal function. Accordingly, a reduced starting dose of ixazomib is recommended in patients with severe renal impairment and ESRD requiring dialysis. Unbound systemic exposures of ixazomib are 27% higher in patients with moderate or severe hepatic impairment as compared to patients with normal hepatic function. A reduced starting dose of ixazomib is recommended for patients with moderate or severe hepatic impairment.

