15.2 Pomalidomide (Pomalyst®, CC-4047)

Please consult the most current Investigator's Brochure and package insert for complete drug information.

15.21 **Background:** Pomalidomide (CC-4047) is a novel drug in the class of immunomodulatory agents known as IMiDs compounds. Pomalidomide binds to its molecular target cereblon (CRBN), a protein that is part of an E3 ubiquitin ligase complex, which is responsible for the poly-ubiquitination of substrate proteins, targeting them for subcellular redistribution and destruction by the proteasome. The pharmacologic properties of pomalidomide are of potential therapeutic benefit in the treatment of various hematologic neoplasms (such as multiple myeloma and myeloproliferative neoplasm-associated myelofibrosis), non-neoplastic hematologic disorders (such as β -thalassemia and sickle cell disease) and non-hematologic disorders such as systemic sclerosis, as well as solid tumor neoplasms.

15.22 **Formulation:** Pomalidomide (CC-4047) capsules can be 0.5-mg gelatin capsules (size 4 reddish brown), 1-mg hard gelatin capsules (size 4 reddish brown), 2-mg (size 2 reddish-brown), 3-mg and 4-mg hard gelatin capsules (size 2 reddish-brown), and 5-mg hard gelatin capsules (size 1 reddish-brown), containing pomalidomide, mannitol, pregelatinized starch, and sodium stearyl fumarate.

Pomalidomide (CC-4047) capsules are supplied in high density polyethylene (HDPE) containers fitted with induction seals and child-resistant plastic closures or PVC/PCTFE blister with push-through foil.

15.23 **Preparation and storage:** Store drug at controlled room temperature, between 68-77 °F (20-25°C) or as indicated on the manufacturer's label. The expiration date is indicated on the label.

Only enough study drug for one cycle of therapy (one month) may be dispensed.

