15.24 **Administration:** Pomalidomide is administered by mouth at approximately the same time each day with water. Pomalidomide should be taken without food, at least 2 hours before or 2 hours after a meal. Capsules should be swallowed whole, and should not be broken, chewed or opened. If a dose of pomalidomide is missed, it should be taken as soon as possible on the same day. If it is missed for the entire day, it should not be made up. Patients should be instructed never to give this medicinal product to another person and to return any unused capsules to the study doctor at the end of treatment. Patients who take more than the prescribed dose of pomalidomide should be instructed to seek emergency medical care if needed and contact study staff immediately.

15.25 **Pharmacokinetic information:**

a) Absorption – oral absorption has been moderately rapid with first dose- C_{max} occurring in 1.5 to 4 hrs. More than 70% of the pomalidomide dose is absorbed in humans. A high fat meal decreased the rate of absorption but had minimal effect on overall extent of absorption; therefore drug may be administered without regard to food intake.

b) Distribution – Apparent volume of distribution in healthy subjects ranged from 74-138 L across a dose range of 1 to 10 mg daily. Pomalidomide protein binding in human plasma is low to moderate (15.8% for R-enantiomer, 42.2% for S-enantiomer) and the binding is concentration independent in the concentration range of 30 and 1000 ng/mL. Drug distributes into semen.

c) Metabolism - Eight metabolites were detected in plasma, each at exposures <10% of the plasma pomalidomide. CYP-dependent metabolites accounted for approximately 43% of the excreted radioactivity, while non-CYP dependent hydrolytic metabolites accounted for 25%, and excretion of unchanged pomalidomide accounted for 10%.

d) Excretion – In healthy patients, 72.8% of the dose was recovered in urine and 15.5% was recovered in feces. Less than 3 % of the dose is excreted as unchanged pomalidomide in the urine. The geometric mean terminal elimination was approximately 7.5 hours.

15.26 **Potential Drug Interactions:** Pomalidomide is partially metabolized by CYP1A2 and CYP3A. Pomalidomide is also a substrate for P-glycoprotein (P-gp).

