15.3 Dexamethasone for Oral Administration (DXM)

- 15.31 **Background:** Dexamethasone is an adrenal corticosteroid compound. Dexamethasone decreases inflammation by suppression of neutrophil migration, decreased production of inflammatory mediators, and reversal of increased capillary permeability; suppresses normal immune response. Dexamethasone's mechanism of antiemetic activity is unknown.
- 15.32 **Formulation:** Commercially available for oral administration as:
Tablets [scored]: 0.5 mg, 0.75 mg, 1 mg, 1.5 mg, 2 mg, 4 mg, and 6 mg
Solution, oral: 0.5 mg/mL (500 mL)
Solution, oral concentrate: Dexamethasone Intensol: 1 mg/mL (30 mL)
- 15.33 **Preparation, storage, and stability:** Refer to package insert for complete preparation and dispensing instructions. Store oral tablets at room temperature between 20°C to 25°C (60°F to 77°F). Protect from moisture. Dispense in a well-closed, light-resistant container as defined in the USP/NF. Store oral liquid at room temperature, do not freeze. Do not use

if solution contains a precipitate. Refer to commercial package for drug expiration date.

15.34 **Administration:** Refer to the treatment section for specific administration instructions. May be taken with meals to decrease GI upset.

15.35 **Pharmacokinetic information:**

Onset of action: Prompt

Duration of metabolic effect: 72 hours

Metabolism: Hepatic

Half-life elimination: Normal renal function: 1.8-3.5 hours; **Biological half-life:** 36-54 hours

Time to peak, serum: Oral: 1-2 hours

Excretion: Urine and feces

15.36 Potential Drug Interactions:

Cytochrome P450 Effect: Substrate of CYP3A4 (major); **Induces** CYP2A6 (weak), 2B6 (weak), 2C8 (weak), 2C9 (weak), 3A4 (strong)
Increased Effect/Toxicity: Aprepitant, azole antifungals, calcium channel blockers, cyclosporine, estrogens, and macrolides may increase the serum levels of corticosteroids. Corticosteroids may increase the hypokalemic effects of amphotericin B or potassium-wasting diuretics (loop or thiazide); monitor. Refer to the package insert for a listing of other drugs.

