Appendix II Patient Medication Diary

Name _____ Study ID Number _____

Please complete this diary on a daily basis. Write in the amount of the dose of pomalidomide, ixazomib, and dexamethasone that you took in the appropriate “Day” box.

On the days that you do not take any study drug, please write in “0”. If you forget to take your daily dose, please write in “0”, but remember to take your prescribed dose at the next regularly scheduled time.

Please drink at least 6 to 8 cups of liquid per day to help drug absorption. Swallow pills whole, with water, and do not to break, chew, crush or open the pills. Study drug should be taken on an empty stomach (no food or drink) at least 1 hour before or 2 hours after a meal. Each pill should be swallowed separately with a sip of water. A total of approximately 8 ounces (240 mL) of water should be taken with the pills.

If you experience any health/medical complaints or take any medication other than pomalidomide, ixazomib, or dexamethasone, please record this information.

Week of: _____

Study Drug	Day 1	Day 2	Day 3	Day 4	Day 5	Day 6	Day 7
Pomalidomide							
Ixazomib							
Dexamethasone							

Week of: _____

Study Drug	Day 8	Day 9	Day 10	Day 11	Day 12	Day 13	Day 14
Pomalidomide							
Ixazomib							
Dexamethasone							

Week of: _____

Study Drug	Day 15	Day 16	Day 17	Day 18	Day 19	Day 20	Day 21
Pomalidomide							
Ixazomib							
Dexamethasone							

Week of: _____

Study Drug	Day 22	Day 23	Day 24	Day 25	Day 26	Day 27	Day 28
Pomalidomide							
Ixazomib							
Dexamethasone							

Patient Signature: _____

My next scheduled visit is: _____
 If you have any questions, please call: _____
 Bring *all* bottles and any unused study medication along with this diary when you return for your next appointment.

Study Coordinator Use Only		
Number of pills returned	Number of vials returned:	
Discrepancy Yes ___/No ___	Verified by _____	Date _____

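### The patient diary puts all three drugs under ixazomib's fasting rule, which withdraws the with-meals option that Section 15.34 gives for dexamethasone

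*Combined protocol and SAP*

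**What the plan says.** Appendix II instructs the patient: "Study drug should be taken on an empty stomach (no food or drink) at least 1 hour before or 2 hours after a meal". The same page asks the patient to record doses of all three drugs. It lists all three as rows under the study-drug column and treats anything else as other medication.

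The drug-specific text differs by agent:

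- **Ixazomib.** Section 7.3: "The ixazomib should be taken on an empty stomach, at least 1 hour before or no sooner than 2 hours after a meal". Section 15.14 gives the same intervals, and Section 15.15 supplies the reason: "A high-fat meal decreased both the rate and extent of absorption".
- **Dexamethasone.** Section 15.34: "May be taken with meals to decrease GI upset". That section refers to the treatment section for specific instructions, but Section 7 sets no food rule for dexamethasone.
- **Pomalidomide.** Section 15.24: "Pomalidomide should be taken without food, at least 2 hours before or 2 hours after a meal". Section 15.25, however, says that a high-fat meal slowed absorption but "had minimal effect on overall extent of absorption; therefore drug may be administered without regard to food intake". Section 15.2 sends the reader to the current Investigator's "Brochure and package insert for complete drug information".

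**The concern.** The diary is a form that patients complete day by day, so its wording can shape how they take the drugs. A patient who follows it takes dexamethasone, 40 mg at the starting dose, on an empty stomach every time. The protocol's own drug section allows meals precisely to lessen gastrointestinal upset.

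The setting gives that option some value. Section 15.37 lists esophagitis and peptic ulcer among dexamethasone's toxicities, and Section 9.9h puts patients on daily aspirin 325 mg. Table 8.4 deals with dexamethasone-related stomach events only after they appear: acid suppression first, then dose reduction or omission. Allowing a meal is a simple preventive step that the protocol already accepts. What is at stake is a small matter of tolerability.

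**Working it through.** The plan states no figure to reproduce. The check compares the food rules and counts scheduled days.

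**Step 1. Food rules side by side.**

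| Drug | Diary | Drug's own section | Comparison |
|---|---|---|---|
| Ixazomib | ≥1 h before or 2 h after a meal | ≥1 h before or ≥2 h after (7.3, 15.14) | Same |
| Dexamethasone | ≥1 h before or 2 h after a meal | With meals allowed (15.34) | Diary narrower |
| Pomalidomide | ≥1 h before or 2 h after a meal | 2 h before or 2 h after (15.24); food immaterial (15.25) | Diary looser than 15.24 before a meal, stricter than 15.25 |

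For pomalidomide, the gap after a meal is 2 h in both the diary and 15.24, so those agree. The only conflict with 15.24 is the interval from 1 h to 2 h before a meal, which the diary permits and 15.24 does not.

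**Step 2. Days on which the dexamethasone restriction applies.** Inputs are the starting schedule in Tables 7.1 and 8.1.

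- Ixazomib: Days 1, 8, 15
- Pomalidomide: Days 1 to 21
- Dexamethasone: Days 1, 8, 15, 22

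Dexamethasone days shared with ixazomib: {1, 8, 15}, so 3 of 4. On these days one fasting rule can be defended as protecting ixazomib absorption. Dexamethasone days with no other study drug scheduled: {22}, so 1 of 4. There the rule has no co-administered drug to protect.

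**Step 3. Can the two rules coexist on a shared day?** Let ixazomib be taken at time T. To stay clear of food on both sides, the previous meal is no later than T − 2 h and the next no earlier than T + 1 h. Dexamethasone taken with that next meal satisfies both 7.3 and 15.34. The two meals need to be 2 + 1 = 3 h apart, which an overnight fast meets. If pomalidomide is taken together with ixazomib and 15.24 is upheld, the next meal moves to T + 2 h and the spacing becomes 2 + 2 = 4 h, which an overnight fast also meets.

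**The case against.** The case for leaving the diary alone has real force. Section 15.34 says dexamethasone may be taken with meals, not that it must, so the diary narrows an option and breaches nothing. One rule for every capsule and tablet is a reasonable simplification in a three-drug oral regimen. It also protects the drug for which these documents report a lower extent of absorption after a high-fat meal. Table 8.4 already manages stomach events. A more elaborate diary carries some risk that ixazomib is taken with food.

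Most of this stands, and it sets the weight of the point. It does not explain Day 22, and on the other three days the two rules are compatible. The risk to ixazomib can be controlled by giving it its own fasting line.

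Three stronger readings are tempting and are not supported:

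- A reader might infer that most dosing is wrongly instructed, since 21 pomalidomide and 4 dexamethasone doses make 25 of the 28 scheduled per cycle. That count measures no harm. The 21 differ only if 15.24 is the benchmark, 15.25 says food does not matter, and the other 4 are a narrowed option.
- A reader might infer that the diary compromises pomalidomide exposure. Section 15.25 reports a minimal effect of a high-fat meal on the extent of absorption, so no such consequence follows.
- A reader might infer that patients receive no other guidance on food. Section 15.13 calls for comprehensive instructions on ixazomib dosing, and Appendix IV for a pomalidomide information sheet. Their content is not shown, so it cannot be said whether they address the point.

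**Conclusion.** The point holds as a minor, low-cost improvement. The diary extends a rule that is correct for ixazomib to dexamethasone and so withdraws an option the protocol offers for gastrointestinal comfort. It does so on 4 days per cycle, including Day 22, when no other study drug is scheduled. The tolerability gain from restoring the option is likely small and cannot be quantified from the documents.

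For pomalidomide, the diary, 15.24 and 15.25 give three different answers. This is a wording inconsistency. Which answer is right depends on the Investigator's Brochure and package insert, which are not available here.

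The conclusion assumes that patients read the diary's rule as covering every drug in its grid, and that doses fall on their scheduled days. Section 7.3 allows a missed ixazomib dose to be taken late if the next is at least 72 h away, so a make-up dose could fall on Day 22; ixazomib's own fasting rule would then apply. This is not a safety or efficacy defect, and the statistical design is untouched.

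**What to change.** Replace the diary's single food rule with separate lines:

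- **Ixazomib:** empty stomach, at least 1 h before or 2 h after food (unchanged).
- **Dexamethasone:** may be taken with food. On Days 1, 8 and 15, and on any other day ixazomib is taken, use a meal at least 1 h after the ixazomib dose.
- **Pomalidomide:** first reconcile 15.24 with 15.25 against the current Investigator's Brochure or package insert, then carry the agreed wording into the diary. If the 2 h gap before a meal is kept and the two capsules are taken together, the dexamethasone meal should follow by at least 2 h.

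The cost is one revised diary page and one corrected sentence in 15.24 or 15.25. The downside is a slightly longer diary and a small risk that ixazomib is taken with food, which the explicit ixazomib line controls. A detailed day-by-day dosing timetable is not needed.

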Appendix III Drug Classification Guide

Class	Generic name	Other Names
Alkylators		
	Cyclophosphamide	Cytoxan
	Melphalan	Alkeran
	Carmustine	BCNU
	Busulphan	Myleran
	Chlorambucil	
	Cisplatin	
	Dacarbazine	
	Ifosfamide	
	Lomustine	CCNU
	Mecholorethamine	Nitrogen mustard
	Procarbazine	
Antimetabolites		
	Asparaginase	
	Chlorodeoxyadenosine	2-CDA
	Cytabarine	Cytosar-U Tarabine
	Deoxycorormycin	
	Floxuridine	
	Fludarabine	
	Fluouracil	
	Hydroxyurea	
	Mercaptopurine	
	Methotrexate	
	Thioguanine	
	Thiotepa	
Anthracyclines/Antibiotics		
	Bleomycin	
	Dactinomycin	
	Daunorubicin	
	Doxorubicin	Adriamycin
	Pegylated doxorubicin	Doxyl
	Idarubicin	
	Mitomycin	
	Mitoxantrone	
Bisphosphonates		
	Zoledronic acid	Zometa
	Pamidronate	Aredia
Corticosteroids		
	Prednisone	

	Methylprednisolone Dexamthasone	Solumedrol Decadron	Dex
IMiDs (immune modulatory drugs)	Thalidomide Lenalidomide Interferon Pomalidomide Levamisole	Thalidomid Revlimid	CC-5013
Proteasome inhibitors	Bortezomib Carfilzomib MLN9708 Oprozomib	Velcade Kyprolis Ixazomib	
Topoisomerases	Etoposide	VP-16	
Taxanes	Paclitaxel Docetaxel	Taxol	
Monoclonal Antibodies	Anti-SLAMF7 Anti-38	Elotuzumab Daratumumab	
Vinca Alkyloid	Vinblastine Vincristine Vindesine Vinorelbine		

Last Updated 9/29/14

Appendix IV Pomalidomide Education and Counselling Guidance Document

NOTE: This document will be completed as part of the Pomalyst REMS program. It is included here for informational purposes only.

Protocol Number: MC1487_____

Patient Name (Print): _____ DOB: ____/____/____ (mm/dd/yyyy)

(Check the appropriate box to indicate risk category)

Female:

If female, check one:

FCBP (Female of childbearing potential): sexually mature female who: 1) has not undergone a hysterectomy (the surgical removal of the uterus) or bilateral oophorectomy (the surgical removal of both ovaries) or 2) has not been naturally postmenopausal (amenorrhea following cancer therapy does not rule out childbearing potential) for at least 24 consecutive months (i.e., has had menses at any time during the preceding 24 consecutive months)

NOT FCBP

Male:

Do Not Dispense study drug if:

- **The patient is pregnant.**
- **No pregnancy tests were conducted for a FCBP.**
- **The patient states she did not use TWO reliable methods of birth control (unless practicing complete abstinence of heterosexual contact) [at least 28 days prior to therapy, during therapy and during dose interruption].**

FCBP:

1. I verified that the required pregnancy tests performed are negative.
2. I counselled FCBP regarding the following:
 - Potential risk of fetal exposure to pomalidomide: If pomalidomide is taken during pregnancy, it may cause birth defects or death to any unborn baby. Females are advised to avoid pregnancy while taking pomalidomide. The teratogenic potential of pomalidomide in humans cannot be ruled out. FCBP must agree not to become pregnant while taking pomalidomide.
 - Using TWO reliable methods of birth control at the same time or complete abstinence from heterosexual contact [at least 28 days prior to therapy, during therapy, during dose interruption and 28 days after discontinuation of study drug].
 - That even if she has amenorrhea she must comply with advice on contraception.

- Use of one highly effective method and one additional method of birth control AT THE SAME TIME. The following are examples of highly effective and additional effective methods of contraception:
 - Highly effective methods:
 - Intrauterine device (IUD)
 - Hormonal (birth control pills, injections, implants)
 - Tubal ligation
 - Partner's vasectomy
 - Additional effective methods:
 - Male condom
 - Diaphragm
 - Cervical Cap
 - Pregnancy tests before and during treatment, even if the patient agrees not to have reproductive heterosexual contact. Two pregnancy tests will be performed prior to receiving study drug, one within 10-14 days and the second within 24 hours of the start of study drug.
 - Frequency of pregnancy tests to be done:
 - Every week during the first 28 days of this study and a pregnancy test every 28 days during the patient's participation in this study if menstrual cycles are regular or every 14 days if cycles are irregular.
 - If the patient missed a period or has unusual menstrual bleeding.
 - When the patient is discontinued from the study and at day 28 after study drug discontinuation if menstrual cycles are regular. If menstrual cycles are irregular, pregnancy tests will be done at discontinuation from the study and at days 14 and 28 after study drug discontinuation.
 - Stop taking study drug immediately in the event of becoming pregnant and to call their study doctor as soon as possible.
 - NEVER share study drug with anyone else.
 - Do not donate blood while taking study drug and for 28 days after stopping study drug.
 - Do not breastfeed a baby while participating in this study and for at least 28 days after study drug discontinuation.
 - Do not break, chew, or open study drug capsules.
 - Return unused study drug to the study doctor.
3. Provide Pomalidomide Information Sheet to the patient.

FEMALE NOT OF CHILDBEARING POTENTIAL (NATURAL MENOPAUSE FOR AT LEAST 24 CONSECUTIVE MONTHS, A HYSTERECTOMY, OR BILATERAL OOPHORECTOMY):

1. I counselled the female NOT of childbearing potential regarding the following:
 - Potential risk of fetal exposure to pomalidomide (Refer to item #2 in FCBP)
 - NEVER share study drug with anyone else.
 - Do not donate blood while taking study drug and for 28 days after stopping study drug.
 - Do not break, chew, or open study drug capsules
 - Return unused study drug capsules to the study doctor.
2. Provide Pomalidomide Information Sheet to the patient.

MALE:

1. I counselled the Male patient regarding the following:
 - Potential study drug fetal exposure to pomalidomide (Refer to item #2 in FCBP).
 - To engage in complete abstinence or use a condom when engaging in sexual contact (including those who have had a vasectomy) with a pregnant female or a female of childbearing potential, while taking study drug, during dose interruptions and for 28 days after stopping study drug.
 - Males should notify their study doctor when their female partner becomes pregnant and female partners of males taking study drug should be advised to call their healthcare provider immediately if they get pregnant
 - NEVER share study drug with anyone else.
 - Do not donate blood while taking study drug and for 28 days after stopping study drug.
 - Do not donate semen or sperm while taking study drug and for 28 days after stopping study drug.
 - Do not break, chew, or open study drug capsules.
 - Return unused study drug capsules to the study doctor.
2. Provide Pomalidomide Information Sheet to the patient.

Investigator/Counselor Name (Print): _____
(circle applicable)

Investigator/Counselor Signature: _____ Date: ____ / ____ / ____
(circle applicable)

